At Visit 3, BP will be assessed, and controlled patients will continue the same extemporaneous combination from ZOF/AML 30/5 mg, while uncontrolled patients (SBP/DBP >130/80 mmHg) will be up titrated to ZOF/AML 30/10 mg for a further 4 weeks

Visit 4 (Week 8 ± 2 days)

The following procedures/assessments will be performed at Visit 4:

- Recording of concurrent diseases and medical conditions
- Concomitant medications
- Vital sign measurements
- Physical Examinations
- BP Measurement
- ECG
- Perform Urine Pregnancy Test (UPT)
- Perform Local Laboratory Tests
- Patient's instruction to use the automatic blood pressure device, including patient's diary to be returned at site by the patient
- Patients return of the automatic BP device to the site
- Study Drug Compliance assessment [extemporaneous combination of ZOF 30 mg and AML 5 mg/10 mg) return (also empty blisters) and IP accountability]
- AEs and serious adverse events (SAEs) assessment: In case of any patients having an ongoing AE or SAE at the end of the treatment, there will be a follow-up telephone call after 2 weeks to ensure patient safety

The Investigator is expected to record any AE which was ongoing at the last treatment dose and a follow-up phone call should be made after 2 weeks from the last study visit.

In case of an ongoing AE, the Investigator is expected to follow-up until the outcome of the AE has been determined.

MEVARINI	Corporate Medical Department		
Identification Number	Version Number	State	Effective date
FORM-000050125	2.0, CURRENT	Effective	08, Jan 2021

Sponsor: Menarini International Operations Luxembourg SA Study Code: MEIN/20/ZoAm-Hyp/001	Protocol Version 1.0 of 1	23/04/2021

The details of the study visits are described in the Study Flow Chart Section 2.3.

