6.2 Inclusion and Exclusion Criteria

6.2.1 Inclusion Criteria

МЕМАТИИ	Corporate Medical Department		
Identification Number	Version Number	State	Effective date
FORM-000050125	2.0, CURRENT	Effective	08, Jan 2021

Sponsor: Menarini International Operations Luxembourg SA Study Code: MEIN/20/ZoAm-Hyp/001	Protocol Version 1.0 of 1	23/04/2021

A patient will be considered eligible for inclusion in the study only if all the following criteria are met:

- 1. Male or female Grade 1-2 hypertensive patients: with mean sitting SBP ≥140 mmHg and ≤179 mmHg and/or mean sitting DBP ≥ 90 mmHg and ≤109 mmHg at Screening, with ≥18 and ≤65 years of age, on monotherapy either with ZOF 30 mg or AML 5mg or any other ACE-I or CCBs (Felodipine, isradipine, lacidipine, lercanidipine, nicardipine, nifedipine, and nisoldipine) for at least 1 month before Visit 1 (Screening).
- 2. Patients who are able to understand and give written informed consent at Screening
- 3. Patients who are available for the entire trial period and willing to adhere to the protocol requirements
- 4. Ability to take oral medication and willing to adhere to the drug regimen
- 5. Female patients are eligible to participate if not pregnant, or not breastfeeding and must refrain from donating or storing eggs. For females of reproductive potential: use of highly effective contraception (e.g., method of birth control throughout the study period and for 4 weeks after study completion defined as a method which results in a failure rate of less than 1% per year) such as:
 - Combined (estrogen- and progestogen-containing) hormonal contraception associated with inhibition of ovulation (oral, intravaginal, transdermal)
 - Progestogen-only hormonal contraception associated with inhibition of ovulation (oral, injectable, implantable)
 - Intrauterine device (IUD)
 - Intrauterine hormone-releasing system (IUS)
 - Bilateral tubal occlusion
 - Vasectomized partner (performed at least 2 months before screening) (if the partner is the sole sexual partner of the trial participant and that the vasectomized partner has received medical assessment of the surgical success)
- 6. A male patient must agree to use contraception during the whole study period and for at least 1 week after the last dose of study treatment and refrain from donating sperms during this period

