9.9 Collection, Recording and Reporting of AEs

At each visit the Investigator will collect and assess any occurred subjective or objective AE occurred to each subject after his / her signature of the informed consent.

The Investigator should manage as AE any laboratory test abnormality (newly occurring after the IMP administration or worsening of previously known abnormalities) considered as clinically relevant: i.e. values significantly above or under normal range or which require an intervention or diagnostic tests, or may result in the IMP discontinuation.

Any AE communicated by the subject or by the subject's relatives or delegates through phone calls, letters or e-mails will also be collected and assessed.

The Investigator shall record on the respective eCRF AE recording pages / AE form any recognised AE identifying an ICSR, both serious and non-serious, whether or not thought to be drug-related, observed in or reported by the subject (or relatives / delegates), specifying the judgement on the causal relationship with the study treatment.

Any available information and diagnostic measure (laboratory and instrumental tests, procedures, etc.) shall be recorded in and / or attached to the concerned eCRF pages / sections.

HENYBINI	Corporate Medical Department		
Identification Number	Version Number	State	Effective date
FORM-000050125	2.0, CURRENT	Effective	08, Jan 2021

The Investigator is expected to also record any AE which was ongoing at the last treatment dose and a follow-up phone call should be made after 2 weeks from the last study visit. The Investigator is expected to follow up any AE occurred during the study, including the follow-up period, until the outcome of the AE has been determined.

The Investigator must report all the collected information on any ICSR with Serious and Non Serious AE (whether or not thought to be related to the investigational drug), providing the *concerned eCRF-AE pages/ by alert email*), after the first knowledge of the occurrence of the case, to:

CRO Pharmacovigilance Officer:

Email: MEIN/20/ZoAm-Hyp/[contact]

[contact] [contact]

Mobile: N/A

When relevant, also the eCRF pages concerning medical history, concomitant medication, and laboratory tests will be placed at Sponsor disposal by email.

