9.13 Management of pregnancy exposure cases

The Investigator is expected to record in the provided form (Pregnancy Exposure Form)any case of pregnancy exposure occurring in a female subject or in a male subject's partner during the treatment and follow-up periods, sending it within 5 days after being made aware of the pregnancy, to the CRO *by email*, to be forwarded to the Sponsor.

The Investigator is requested to follow each case of pregnancy exposure until the outcome. If the pregnancy results in an abnormal outcome, this will be recorded in the eCRF as a SAE and managed as above described.

Eligibility of a woman of childbearing potential (WOCBP) will be considered as described in Section 6.2.

A woman is considered fertile following menarche and until becoming postmenopausal unless permanently sterile as described below.

Women in the following categories are not considered WOCBP if:

- Premenarchal
- Premenopausal female with one of the following:
 - o Documented hysterectomy.
 - o Documented bilateral salpingectomy.
 - o Documented bilateral oophorectomy.

Note: Documentation can come from the study centre personnel's: review of the patient's medical records, medical examination, or medical history interview.

Postmenopausal female: A postmenopausal state is defined as no menses for 12 months without an alternative medical cause. A high follicle stimulating hormone (FSH)

МЕМАТИИ	Corporate Medical Department		ent
Identification Number	Version Number	State	Effective date
FORM-000050125	2.0, CURRENT	Effective	08, Jan 2021

level to 30 mIU/mL or higher may be used to confirm a postmenopausal state in women not using hormonal contraception or hormonal replacement therapy (HRT). However, in the absence of 12 months of amenorrhea, a single FSH measurement is insufficient. Females on HRT and whose menopausal status is in doubt will be required to use one of the non-estrogen hormonal highly effective contraception methods if they wish to continue their HRT during the study. Otherwise, they must discontinue HRT to allow confirmation of postmenopausal status before study enrolment.

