13 STUDY DISCONTINUATION AND CLOSURE

Menarini International Operations may discontinue this study prematurely for reasonable cause. Possible reasons for early termination or temporary suspension of the study include, but is not limited to:

- Study closure based on PI decision and/or
- Study closure based on Sponsor decision and/or
- Study closure based on Regulatory or other oversight bodies initiation and/or
- Review of serious, unexpected, and related AEs and/or
- Non-compliance.

In case this study was temporarily suspended or prematurely terminated, written notification documenting the reason for study suspension or termination will be provided by the suspending or terminating party at a reasonable time in advance of the intended termination.

The Investigator may also discontinue this study at his/her site for reasonable cause after notifying the IEC and providing written notice to Menarini International Operations at a reasonable time in advance of the intended termination.

Please note advanced notice is not required by either party if the study is stopped due to safety concerns.

Menarini International Operations and the Investigator should take the following steps to follow up on patient safety and ensure data integrity:

- Immediately notify the pharmacovigilance officer at Biorasi
- Notify the IEC within 24 hours
- Contact all patients by phone and distribute written communication that the study has been stopped
- Advise all patients to report for an early termination visit
- Make plans to follow all patients for AEs for two months after the study has been stopped or for as long as it takes for any AE/SAEs to resolve, whichever is longer
- Instruct study staff to enter all data in the case report form and ensure their completion

MENARINI	Corporate Medical Department		
Identification Number	Version Number	State	Effective date
FORM-000050125	2.0, CURRENT	Effective	08, Jan 2021

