### 8.2 Adverse Events, Adverse Drug Reactions, and Deaths

Adverse Events (AEs) are any untoward medical occurrence in a clinical trial patient administered a medicinal product and which does not necessarily have a causal relationship with this treatment.

*Treatment Emergent AEs (TEAEs)* are defined as AEs that occur only once treatment has started (after the first dose of monotherapy of ZOF or AML). Thus, all AEs that occur in both the monotherapy and combined therapy periods will be considered treatment-emergent.

Adverse Drug Reactions (ADRs) are defined as AEs that have a relationship of "certain," "probable," "possible," or "unassessable."

All AEs will be coded using the Medical Dictionary for Regulatory Activities (MedDRA) version 24.1 or later.

The following tabulations will be produced for the monotherapy period and the combination therapy periods for the SAF population:

- Monotherapy Period (Day of Visit 1 through day before Day of Visit 2)
  - All treatment-emergent AEs (TEAEs)

- Severe TEAEs
- Adverse Drug Reactions (ADRs)
- TEAEs leading to study discontinuation
- Serious TEAEs (TESAEs)
- o Serious ADRs
- TESAEs with outcome of death
- Combination Therapy Period (Day of Visit 2 through Day of Visit 4)
  - All treatment-emergent AEs (TEAEs)
  - Severe TEAEs
  - Adverse Drug Reactions (ADRs)
  - TEAEs leading to study discontinuation
  - Serious TEAEs (TESAEs)
  - Serious ADRs
  - TESAEs with outcome of death

Key guidelines for counting incidence proportions of AEs/TEAEs/ADRs (collectively referred to as AEs for the remainder of this section) are as follows:

- When a patient has the same AE reported multiple times during an analysis period based on MedDRA terminology (SOC or PT), the patient will only be counted once within a level of MedDRA in an AE incidence table.
- When assessing investigator reported relationship to study drug of the AEs, if an AE reported multiple times changes in causal relationship during an analysis period for a patient, the event with highest relatedness will be presented. Related AEs (i.e., ADRs) will include those reported as "certain," "probable," "possible," or "unassessable" by the investigator.

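### SAP 8.2 closes its adverse-event tables on the day of Visit 4, so an event recorded with later onset is listed but counted in no incidence table

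*SAP*

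**What the plan says.** **SAP 8.2, definition.** Treatment-emergent AEs (TEAEs) "are defined as AEs that occur only once treatment has started (after the first dose of monotherapy of ZOF or AML". That sentence gives a start and no end. The next one adds that "all AEs that occur in both the monotherapy and combined therapy periods will be considered treatment-emergent".

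**SAP 8.2, tables.** Seven tabulations are planned for each of two periods: all TEAEs, severe TEAEs, adverse drug reactions, TEAEs leading to discontinuation, serious TEAEs, serious drug reactions, and serious TEAEs with outcome of death. The monotherapy period ends the day before Visit 2. The other is the "Combination Therapy Period (Day of Visit 2 through Day of Visit 4". There is no third period.

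**SAP listings.** All AEs are listed by patient for the Safety Population. Listing 16.2.7.1 has a therapy-period column with two codes, monotherapy and combined therapy. Deaths have their own Listing 16.2.7.3.

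**Protocol, after the last visit.** Section 9.9 asks for a call 2 weeks after the last study visit and states: "The Investigator is expected to follow up any AE occurred during the study, including the follow-up period", until the outcome is known. In the Visit 4 list of Section 5.1, the call is made "In case of any patients having an ongoing AE or SAE at the end of the treatment". Section 9.13 has pregnancy exposure recorded "during the treatment and follow-up periods". Section 12.7 ends the study at the last subject's Week 8 visit.

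**The concern.** The protocol foresees events after Visit 4, and the SAP has nowhere to count them. The cut-off applies equally to the serious and fatal tabulations. SAP 8.1.4.2 counts planned doses up to the day before Visit 4, so the tables close about one day after the last planned combination dose. A serious event starting a few days later would be visible to someone reading the listings line by line, but not in the incidence summaries on which the safety conclusion will rest.

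A second problem sits upstream. If sites read the follow-up passages differently, whether a late event is asked about at all depends on the passage a site follows. An event that nobody solicits and the patient does not volunteer reaches neither table nor listing.

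**Working it through.** The plan states no figure on this point to reproduce, and the documents give no event rates. The check is to trace cases through the rules and then set the follow-up passages side by side. I take the date of an event to be its onset date; SAP 8.2 says only that events occur in a period.

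**Case A: AE starts before Visit 4 and is still ongoing there.** Onset lies in the combination period, so it is tabulated whatever its end date. The 2-week call adds outcome information only. No gap.

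**Case B: serious AE starts 5 days after Visit 4.**
- Recorded? Section 9.9 supports this through its reference to the follow-up period.
- TEAE? Yes by the opening sentence of the definition. The next sentence mentions only the two table periods, so it does not settle the question.
- Table? None. Visit 4 + 5 days is later than the day of Visit 4.
- Listing? Yes, but neither code in Listing 16.2.7.1 fits the date.

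**Case C: as B, but fatal.** It is absent from the table of serious TEAEs with outcome of death and present in Listing 16.2.7.3.

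**Case D: patient stops early in the combination period and an AE starts after the early termination visit.** Protocol 2.2 and 10 provide that visit, and 2.2 gives it all Visit 4 assessments. SAP 8.2 names only Visit 4 as the closing date. If the termination visit stands in for Visit 4, the result is the same as in B. A patient withdrawn during or at the end of run-in raises the same question for the monotherapy period.

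**Day count.** Table coverage after Visit 4: 0 days. Follow-up call: Visit 4 + 14 days. A new event reported at that call has no table.

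**Protocol passages side by side.**
- *Who is contacted.* One bullet in 5.1 limits the call to patients with an ongoing AE or serious AE. A later sentence in 5.1, note e to the flow chart in 2.2, and 9.9 mention the call without that limit, though next to the recording of AEs ongoing at the last dose. Section 10 bars further attempts to contact withdrawn patients unless safety findings require it.
- *What is recorded.* Note e and 5.1 speak of ongoing AEs. Only the follow-up phrase in 9.9 reaches new ones.
- *How long.* Sections 9.9 and 9.13 use a follow-up period whose length is nowhere stated. Section 12.7 places the end of study at Visit 4.
- *Pregnancy.* Section 6.2.1 requires, for females of reproductive potential, a "method of birth control throughout the study period and for 4 weeks after study completion". The recording window in 9.13 depends on the undefined follow-up length, so the two cannot be compared until that is set.

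**The case against.** The best reply is that nothing recorded is lost. AEs are listed with no Visit 4 cut-off, deaths have a listing, serious AEs go to the CRO within 24 hours (Protocol 9.10.1), and 9.9 accepts AEs reported by phone, letter or e-mail. This stands. It confines the effect on recorded events to the incidence tables, but those tables are the summary of safety.

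It can also be said that the second sentence of the TEAE definition limits treatment emergence to the two periods. That is a possible reading. It would make the omission deliberate but unstated, and the SAP would still need to say so.

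Stronger conclusions are tempting and are not supported:
- *The protocol collects AEs for two more weeks.* No passage says this. The call is tied to AEs ongoing at the last dose; new-onset collection rests on one phrase in 9.9.
- *Early stoppers have no closing visit.* They do (2.2, 10), and SAP 5.2.4 puts early termination visits in the summary tables. Only the date rule in 8.2 is missing.
- *The tables omit 14/(56 + 14) = 20% of the observation window.* This assumes a 14-day follow-up period that is never defined, and it is a share of time, not of events.
- *Pregnancy recording misses 14 of the 28 days after completion, or covers none of them.* Both figures assume a follow-up length that 9.13 does not give; at 4 weeks or more there is no gap.
- *Section 13 sets a competing window.* Its instruction, "Make plans to follow all patients for AEs for two months after the study has been stopped", applies only to a stopped study.

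Finally, SAP 8.2 assigns the whole day of Visit 2 to the combination period, although 5.2.1 places the first combination dose after that visit's assessments. This can add events to the combination tables. It is a separate matter and does not restore events lost at the other end.

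**Conclusion.** The point holds for the tables and for the inconsistency of the follow-up passages. Under SAP 8.2 as written, any AE, serious AE or fatal serious AE recorded with onset after Visit 4 (or after the early termination visit, if that stands in for Visit 4) is listed and not tabulated. The direction is certain, since leaving out events can only lower the combination's counts. The size is unknown and may be nil if no late event is recorded. The conclusion rests on periods being applied by onset date. It does not depend on how long the follow-up period was meant to be. On pregnancy, the documents support only a request to reconcile 9.13 with 6.2.1, not a finding that cases will be missed.

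**What to change.** **SAP 8.2.** Extend the combination-period AE tables through the protocol's 2-week follow-up contact. State that the early termination visit replaces Visit 4 for patients who stop early, and apply the same rule to the monotherapy period for patients withdrawn during or after run-in. Give the TEAE definition the same end date. Carry a matching period flag in Listing 16.2.7.1. An acceptable alternative is to leave the period as it is and show events after Visit 4 as a separate row in each table.

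**Protocol.** Reconcile flow-chart note e, 5.1 (Visit 4), 9.9, 9.13, 10 and 12.7 into one definition of the follow-up period: its length, who is contacted, and that new as well as ongoing AEs are recorded. Reconcile the pregnancy recording window in 9.13 with the 4-week window in 6.2.1.

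**Cost.** In the SAP, a date rule, a flag and a few lines of text; this can be applied to whatever has been recorded, even if conduct is complete. In the protocol, a clarification, and a short call to patients without an ongoing AE if the reconciled rule includes them. The downside is that a few background events unrelated to treatment will enter the tables.

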extemporaneous combination for additional 4 weeks \pm 2 days, while uncontrolled patients (sitting SBP/DBP >130/80 mmHg) will be up-titrated from ZOF/AML 30/5 mg to ZOF/AML 30/10 mg for further 4 weeks \pm 2 days.

At Visit 3 patients with SBP/DBP values classified as Grade 3 (SBP \geq 180 or DBP \geq 110 mmHg) hypertension will be withdrawn from the study.

If patients at Visit 3, do not tolerate the extemporaneous combination treatment or they have an adherence range below 80% or superior to 120%, they will be withdrawn from the study. At the end of the assessment period (8 weeks \pm 4 days) at Visit 4, the anti-hypertensive effect of the extemporaneous combination (ZOF/AML 30/5 mg and ZOF/AML 30/10 mg) will be evaluated.

Efforts will be made to achieve 1:1 ratio in the enrolment of patients receiving any ACE-i or allowed CCBs (refer to section Subject Study Phases Duration for allowed CCBs). At Visit 2, a minimum of 45% of uncontrolled patients receiving treatment with ZOF 30 mg or AML 5 mg are required to enter the assessment period, in order to maintain a balance between the 2 treatments during the assessment period.

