#### 3.1.2 Secondary Objectives

- **Objective 2.1**: To assess the antihypertensive efficacy of the extemporaneous combination of ZOF 30 mg in combination with AML 5 mg or AML 10 mg in lowering sitting systolic BP (SBP) between Visit 2 (Week 0) and Visit 4 (Week 8) in patients with uncontrolled BP previously treated with ZOF or AML 5 mg monotherapies for at least 4 weeks.
- **Objective 2.2**: To assess the antihypertensive efficacy of the extemporaneous combination of ZOF/AML 30/10 mg vs. ZOF/AML 30/5 mg, in lowering sitting DBP and SBP between Visit 3 (Week 4) and Visit 4 (Week 8) in patients with uncontrolled BP previously treated with ZOF or AML 5 mg monotherapies for at least 4 weeks.
- **Objective 2.3**: Monotherapy: to evaluate the total number and percentage of patients who achieved the BP goal (sitting BP ≤130/80 mmHg) at Visit 2 (Week 0). Combination therapy: to

evaluate the total number and percentage of patients who achieved the BP goal (sitting BP  $\leq$ 130/80 mmHg) at Visit 3 (Week 4) and Visit 4 (week 8).

- **Objective 2.4**: To assess the compliance to the treatment (percentage of actual doses taken versus doses to be taken) at Visit 2 (Week 0), at Visit 3 (Week 4) and at Visit 4 (Week 8).
- **Objective 2.5**: To evaluate the safety and tolerability of the monotherapies (ZOF 30 mg and AML 5 mg) after 4 weeks of therapy and of the extemporaneous combinations (ZOF 30 mg and AML 5 mg or AML 10 mg) after 8 weeks of treatment.

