### 5.5 Reporting Conventions

The following conventions will be used across all study summaries and analyses, unless otherwise specified in the corresponding section.

- Summary statistics will consist of sample size (n), mean, standard deviation (SD), median, minimum (min), and maximum (max) values for continuous and some ordinal variables; and sample size (n), frequencies, and percentages (%) for categorical and some ordinal variables.
- Statistical tests and confidence intervals (CI) will be two-sided unless otherwise specified; statistical tests will use an alpha threshold of 0.05 and CIs will use 95% confidence unless otherwise specified.
- Mixed Models for Repeated Measures (MMRM) will be fit using the unstructured covariance matrices. In the event of lack of model convergence, other covariance structures may be used.
- P-values will be calculated to three decimal places. P-values less than 0.001 will be presented as "< 0.001."

Unless otherwise specified, descriptive summary tables will be structured with a column for each monotherapy group (ZOF 30 mg or AML 5 mg) or combined treatment group (ZOF/AML 30/5 mg or ZOF/AML 30/10 mg) and overall (All Patients) and will include the total population size for each group in the header. Conversely, inferential summary tables will use only the All Patients column, unless otherwise specified, to prevent overinflation of the type I error rate.

For descriptive summary tables, patients will be classified as either ZOF/AML 30/5 mg or ZOF/AML 30/10 mg such that no patients are counted in both groups. That is, even though patients in the ZOF/AML 30/10 mg group are also exposed to the ZOF/AML 30/5 mg treatment, they will only be included in the ZOF/AML 30/10 mg and All Patients columns within the summary tables, and not within the ZOF/AML 30/5 mg column.

Summary tables will also indicate the number of patients with complete data for each measurement, event, or outcome.

Data listings will be sorted by treatment group, patient, and visit (when applicable).

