- When summarizing severity of the AEs (mild, moderate, severe), if there are multiple AEs of the same preferred term but different severity during an analysis period for a patient, the AE with the maximum severity will be reported. If the AE term (SOC and PT) is reported more than once, one of them with missing severity, and at least another with non-missing severity, the maximum severity will be chosen from the non-missing severity and the missing severity can be ignored. If all are of missing severity, then the AE severity will be summarized with an additional "Missing" category. In summary of severe AEs, missing severity will be included in severe category following the conservative approach.

All AE tabulations for the monotherapy period will present the incidences separately for the monotherapy groups (ZOF 30 mg or AML 5 mg) and All Patients for the SAF population. That is, all patients who experienced at least one AE in the monotherapy period will be summarized together in the All Patients column of the corresponding summary tables. All patients who take ZOF 30 mg will be summarized in the ZOF 30 mg column and all patients who take AML 5 mg will be summarized in the AML 5 mg column.

All AE tabulations for the combined therapy period will present the incidences separately for the combined treatment groups (ZOF/AML 30/5 mg or ZOF/AML 30/10 mg) and All Patients for the SAF population. That is, all patients who experienced at least one AE in the combined therapy period will be summarized together in the All Patients column of the corresponding summary tables. All patients who take ZOF/AML 30/10 mg will be summarized in the ZOF/AML 30/10 mg column, even for AEs that occurred while taking the ZOF/AML 30/5 regimen. Lastly, all patients who take ZOF/AML 30/5 mg for the duration of the combined therapy period will be summarized in the ZOF/AML 5 mg column.

In summaries by SOC and PT (for both monotherapy and combined therapy periods), AEs will be sorted by descending frequency for SOC and PT in the All Patients column. All AEs will also be presented in bypatient data listings for Adverse Events for the SAF population.

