## 2.1.3 Safety

Table 14.3.1.1.1
Overall Summary of Treatment Emergent Adverse Events - Monotherapy Period
(Safety Population)

		ZOF 30 mg	AML 5 mg	All Patients
Adverse Events [1,2,3,4]	Statistic	(N=xx)	(N=xx)	(N=xx)
Total Number of TEAEs	n	xx	xx	xx
Total Number of TESAEs	n	xx	xx	xx
Total Number of ADRs	n	XX	XX	хх
Number of Patients with:				
At Least One TEAE	n (%)	xx (xx.x)	xx (xx.x)	xx (xx.x)
At Least One Severe TEAE	n (%)	xx (xx.x)	xx (xx.x)	xx (xx.x)
At Least One ADR	n (%)	xx (xx.x)	xx (xx.x)	xx (xx.x)
At Least One TEAE Leading to Study Discontinuation	n (%)	xx (xx.x)	xx (xx.x)	xx (xx.x)
At Least One TESAE	n (%)	xx (xx.x)	xx (xx.x)	xx (xx.x)
At Least One Serious ADR	n (%)	xx (xx.x)	xx (xx.x)	xx (xx.x)
At Least One TESAE with Outcome of Death	n (%)	xx (xx.x)	xx (xx.x)	xx (xx.x)

[1] AE: Adverse Event. Defined as any untoward medical occurrence in a clinical trial patient administered a medicinal product and which does not necessarily have a causal relationship with this treatment.

[2] TEAE: Treatment Emergent Adverse Event. Defined as AEs that occur after the first dose of monotherapy of ZOF or AML.

[3] TESAE: Treatment Emergent Serious Adverse Event.

[4] ADR: Adverse Drug Reaction. Defined as AEs that have a relationship of "certain," "probable," "possible," or "unassessable."

Source: Listings 16.2.7.1, 16.2.7.2, 16.2.7.3

Program Name: XXXX.SAS

Date: DDMMMYYYY

Programming Note:

• For the combined therapy period table presented in the list below: Patients will be classified as either ZOF/AML 30/5 mg or ZOF/AML 30/10 mg such that no patients are counted in both groups. That is, even though patients in the ZOF/AML 30/10 mg group are also exposed to the ZOF/AML 30/5 mg treatment, they will only be included in the ZOF/AML 30/10 mg and All Patients columns, not within the ZOF/AML 30/5 mg column. Patients that do not belong to the ZOF/AML 30/5 mg or ZOF/AML 30/10 mg group will be included only in the All Patients column.

• Repeat for the following tables:

- 0 14.3.1.1.2 Overall Summary of Treatment Emergent Adverse Events Combined Therapy Period Safety Population
  - In the column headers, "ZOF 30 mg" and "AML 5mg" will change to "ZOF/AML 30/5 mg" and "ZOF/AML 30/10 mg", respectively.

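### The combined-period AE tables sort patients by final regimen, so neither the 30/5 mg nor the 30/10 mg column gives the AE incidence of its own regimen

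*SAP*

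**What the plan says.** - **Objective.** Objective 2.5 (SAP 3.1.2) begins "To evaluate the safety and tolerability of the monotherapies (ZOF 30 mg and AML 5 mg) after 4 weeks of therapy" and continues with the combinations at either amlodipine strength after 8 weeks.
- **Window.** SAP 8.2 defines one block for the combination: "Combination Therapy Period (Day of Visit 2 through Day of Visit 4"). It is not split at Visit 3, where the dose can change.
- **30/10 mg column.** SAP 8.2 places every up-titrated patient here for all combined-period events, "even for AEs that occurred while taking the ZOF/AML 30/5 regimen". SAP 5.5 has the same rule for descriptive tables in general ("they will only be included in the ZOF/AML 30/10 mg and All Patients columns within the summary tables"), and the programming notes to the AE shells repeat it ("they will only be included in the ZOF/AML 30/10 mg and All Patients columns, not within the ZOF/AML 30/5 mg column").
- **30/5 mg column.** SAP 8.2: "all patients who take ZOF/AML 30/5 mg for the duration of the combined therapy period will be summarized in the ZOF/AML 5 mg column". I read the last label as a misprint for 30/5 mg.
- **Patients in neither group.** The note to shell 14.3.1.1.1, which governs combined-period table 14.3.1.1.2, says: "Patients that do not belong to the ZOF/AML 30/5 mg or ZOF/AML 30/10 mg group will be included only in the All Patients column".
- **Withdrawal at Visit 3.** Protocol 5 withdraws patients at that point for intolerance ("If patients at Visit 3, do not tolerate the extemporaneous combination treatment"), for adherence outside 80% to 120%, and for Grade 3 hypertension.

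**The concern.** SAP 8.2 says that the combined-period tables present incidence separately for the two combination groups. A reader of the study report will take a column headed with a regimen as the AE incidence on that regimen. The rule sorts patients by their Visit 3 outcome instead of sorting events by the treatment in effect when they began. An event in week 2 of an up-titrated patient, before any amlodipine 10 mg was taken, is reported under 30/10 mg. The same patient's 4 weeks on 30/5 mg drop out of the 30/5 mg column.

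At stake is the by-strength description of all TEAEs, severe TEAEs, ADRs and serious events in the combined period. Objective 2.5 is the only safety objective, and it names both strengths.

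**Working it through.** The documents state no AE rate, so there is no planned figure to reproduce. The rates and up-titrated shares below are assumptions. The visit schedule and the figure of 216 patients entering the assessment period come from the protocol and SAP.

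**1. Exposure behind each column.** The schedule is nominally 4 weeks on 30/5 mg, then 4 weeks on 30/5 mg or 30/10 mg. For a completer in the 30/10 mg column, time on 30/5 mg is 4/(4 + 4) = 50%, whatever share is up-titrated. The share f determines how much 30/5 mg time is filed under 30/10 mg. With N = 216 and no dropout:

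share = 4fN / [4N + 4(1 − f)N] = f/(2 − f)

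- f = 0.3: 0.3/1.7 = 17.6%
- f = 0.5: 0.5/1.5 = 33.3%
- f = 0.7: 0.7/1.3 = 53.8%

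**2. Patient incidence in the 30/10 mg column.** Let p5 and p10 be the 4-week risks on 30/5 mg and 30/10 mg, independent between the two intervals.

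- As planned: 1 − (1 − p5)(1 − p10). By regimen at onset: p10.
- Event only on 30/5 mg: p5(1 − p10) of the column. Divided by the planned incidence, this is the share of patients with an event.

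| p5 / p10 | Planned column | By onset | Only on 30/5 mg, of column | Only on 30/5 mg, of patients with an event |
|---|---|---|---|---|
| 5% / 10% | 1 − 0.95 × 0.90 = 14.5% | 10% | 4.5% | 31% |
| 10% / 10% | 1 − 0.90 × 0.90 = 19% | 10% | 9% | 47% |
| 10% / 20% | 1 − 0.90 × 0.80 = 28% | 20% | 8% | 29% |

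The last two columns have different denominators. The 47% is a share of up-titrated patients who had an event, not of all patients in the column.

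**3. Patients who stop on 30/5 mg before or at Visit 3.** Three places do not agree:

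- SAP 8.2 reserves the 30/5 mg column for those on that regimen throughout the combined period, which leaves these patients out.
- The AE shell note then sends them to All Patients only.
- Disposition shell 14.1.1 has a 30/5 mg cell for patients excluded at Visit 3, which puts them in.

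That shell also has a 30/5 mg cell for patients excluded at Visit 2, who never took the combination, so it may be a template slip. In either case the AE tables need an explicit rule.

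**4. Tables affected.** A patient who stops treatment or dies on 30/5 mg never reaches 30/10 mg. The AE-discontinuation table (14.3.1.5.2) and the death table (14.3.2.3.2) therefore carry little or no 30/5 mg content under 30/10 mg. Their weakness is on the 30/5 mg side, through step 3. No 30/10 mg event is filed under 30/5 mg, so that column is incomplete and selected, but not contaminated.

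**5. Would plain percentages by onset be enough?** No, because 30/5 mg follow-up would be 4 weeks for some patients and 8 for others. At 10%/20% the 30/5 mg column by onset shows f × 0.10 + (1 − f) × [1 − 0.90²] = f × 0.10 + (1 − f) × 0.19:

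- f = 0.3: 16.3%, ratio 0.20/0.163 = 1.23
- f = 0.5: 14.5%, ratio 1.38
- f = 0.7: 12.7%, ratio 1.57

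The planned columns give 0.28/0.19 = 1.47, and the assumed 4-week risks give 2.0. Incidence per 4-week interval returns 10% and 20%, ratio 2.0.

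**The case against.** The strongest defence is that this is an openly stated descriptive convention. SAP 5.5 sets out disjoint columns, confines inferential tables to All Patients unless otherwise specified, and promises no test between strengths. Objective 2.5 speaks of the combinations after 8 weeks, and nobody takes 30/10 mg for 8 weeks, so a column by titration path over 8 weeks is a coherent summary. All Patients describes the titrated strategy, and the listings let a reader trace any event.

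Much of this stands. The by-path table answers a real question and can be kept. Three things do not follow from it:

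- The columns are headed by regimen, not by path. The rule sits in the SAP text and programming notes, and no footnote in the AE shells prints it.
- All Patients cannot describe either strength. Read literally, its denominator is the Safety Population, which includes people dosed only in the run-in.
- Listing 16.2.7.1 flags only monotherapy or combined period. Regimen at onset can be derived from the collected dates, but no planned AE table does so.

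**Conclusion.** The concern holds for the combined-period AE tables. As planned, the 30/10 mg column mixes two regimens, with half of each completer's time on 30/5 mg. The 30/5 mg column omits the first 4 weeks of up-titrated patients, and the place of those who stop on 30/5 mg is inconsistent. The 50% follows from the schedule. The incidence figures, such as 28% instead of 20%, rest on assumed 4-week risks, independence between intervals and no dropout.

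A reader might infer more than the documents support:

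- *That Objective 2.5 cannot show the tolerability of either regimen.* Endpoint 2.5 also covers laboratory tests, ECG, vital signs and physical examination (SAP 8). The last two are shown at Visits 3 and 4 within each group (SAP 8.4 and 8.5), so for up-titrated patients the values on each strength are separate.
- *That a planned dose comparison is biased.* No safety contrast of 30/10 mg with 30/5 mg is stated in Objective 2.5 or Protocol 12.5.7. The fault lies in each column's own incidence.
- *That every AE table is equally affected.* The discontinuation and death tables are not (step 4).

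This should be corrected. It does not touch the efficacy analyses.

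**What to change.** In SAP 8.2 and shells 14.3.1.1.2 to 14.3.1.5.2 and 14.3.2.1.2 to 14.3.2.3.2 (combined-period tables), tabulate events by the regimen in effect at onset. The by-final-regimen tables may stay as supplementary.

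- **30/5 mg column:** all patients with at least one 30/5 mg combination dose, including those who stop on it, with events until the first 30/10 mg dose or end of treatment.
- **30/10 mg column:** all patients with at least one 30/10 mg dose, with events from that dose on.
- **Statistics:** number exposed, patient-weeks, and exposure-adjusted rates or incidence per 4-week interval, next to n (%).
- **Footnotes:** the columns overlap, events soon after up-titration may carry over from 30/5 mg, and any dose contrast stays confounded by Visit 3 selection and time order.

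The cost is SAP wording and programming. AE start dates (Listing 16.2.7.1) and dated exposure by amlodipine strength (Listing 16.2.5.2) already exist. Two small conventions are needed. The AE listing gives a start date without a time, so onset on the day of the first 30/10 mg dose needs a rule. SAP 5.6.2 imputes incomplete start dates around the first combination dose only, so a rule is also needed around up-titration. The new columns will not add up to All Patients.
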